6.2.4.2 Needle Breaking

The number and proportion of needle breaking occurrence for each pen needle type will be summarized. In addition, a 95% confidence interval for difference in proportions will be calculated using the score method for independent proportions.

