### **13.3 Statistical Methods**

Descriptive statistics (number of observations, mean, and standard deviation, minimum and maximum) will be calculated and presented for all quantitative responses. Frequency tables with number of observations, percentage of total and 95% confidence interval (score method) for the percentage (as applicable) will be created for discrete responses.

**Analysis for relative VAS pain:** a two-sided 95% confidence interval will be calculated for the average rating. A modeling approach may be used to adjust for the pair order effect, BD order effect within pair (due to the often-observed bias towards favoring the last pen needle used in a pair), abdomen site effect and random subject effect. Results will be tested for non-inferiority, followed by superiority:

---

If the lower bound of the CI is  $> -10\text{mm}$ , we can conclude in non-inferiority  
If the lower bound of the CI is  $> 0\text{mm}$ , we can conclude in superiority

Analysis for injection force via 5-point Likert scale: the responses will be converted to ratings of -2 – 2 (where positive ratings favor BD) and a two-sided 95% confidence interval will be calculated for the average rating. A modeling approach may be used to adjust for the pair order effect, BD order effect within pair, abdomen site effect and random subject effect. Results will be tested for superiority:

If the lower bound of the CI is  $> 0$ , we can conclude in superiority

Responses will also be converted to 3 categories: favoring Terumo Nanopass® (negative ratings), no difference (0 ratings) and favoring BD Nano™ PRO (positive ratings) and the difference in percentage of responses with a preference for BD vs Terumo needle calculated, adjusting for the “no preference” category.

Analysis for needle bending and leaking: analysis will be performed using a binary logistic regression with random subject effect and fixed pen needle effect, pair order effect, PN order effect within pair and abdomen site effect. The average difference in percentage of occurrence with BD PN and Terumo PN will be calculated with 95% confidence interval and assessed for statistical significance. The upper bound of the confidence interval will be compared to 0: superiority will be concluded given that the upper bound of the 95% confidence interval for the difference in proportions is  $< 0\%$ .

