2.3 Study Design

This is a subject partially blinded, block randomized, prospective, single-visit, multi-center study to compare user experiences with BD Nano™ PRO pen needle vs. the thinner commercially available Terumo Nanopass® pen needle. The study will include a minimum of 55 Japanese American study subjects having Type 1 or Type 2 diabetes. Study conduct will consist of one 60 to 120 minute Site visit in which pre-set doses of saline will be abdominally delivered by subjects via a reusable insulin pen device. All pen needles will be attached by Study Staff and pen needle outer cover and inner shield will be removed for subjects. Subjects are to perform 12 injections into the abdomen (6 pairs of injections). Pairs of injections will be evaluated and each pair will contain one BD Nano™ PRO and one Terumo Nanopass® pen needle. Subjects will not see pen needle labels or be informed which pen needle is being used to inject. The BD Nano™ PRO has a distinct configuration and subjects will most likely notice the difference vs the Terumo Nanopass®. Subjects will not be informed of the Terumo Nanopass® brand, length or gauge. The pen needle order within the pairs of injections will be randomized for each subject and the pairs will be randomized to various abdominal injection sites within each subject. Besides being informed of the requirement to insert the pen needles 'straight-in' (perpendicular), subjects will be instructed to use their usual injection technique.

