2.5.3 Exploratory Objectives

No formal acceptance criterion has been established for the following objectives - time to deliver dose, total injection time, and survey responses after all injections completed.

3 Sample Size

Leakage data is currently being used to calculate sample size.

Based on previous study data (BDT-2P00116) where leakage is equal to or greater than 1.5U was observed in 20/298 (6.7%) of injections performed with Terumo Nanopass® and in 3/297 (1%) of injections performed with BD Nano™ PRO, a simulation was performed (code found in SVN repository under DBC-18PENDL01Size Bayesian prior proportion.R) indicating that 292 injections per each pen needle type would provide 90% power to show BD Nano™ PRO superiority to Terumo Nanopass®. If each Subject tests 6 pairs of pen needles, 292 injections per each pen needle requires 49 subjects (rounded to 50 subjects). 50 Subjects will generate data for 600 pen needles: 300 pen needle pairs - 300 BD Nano™ PRO and 300 Terumo Nanopass®. A 10% buffer was added (to compensate for subject attrition or unusable data), leading to a planned enrollment number of 55 subjects.

Pain: Assuming the SD for relative VAS is around 50mm (based on DBC-17NUCLS07), a sample size of 300 pairs (50 Subjects x 6 pairs) has >90% power of passing a -10mm NI criteria, assuming a true average of -0.5mm in favor of Terumo Nanopass® (based on a 2-sided 95% CI for the mean).

4 Intended Statistical Software

This document was generated with R version 3.5.1 (2018-07-02) and the following packages (version) were used: assertthat (0.2.0), base (3.5.1), BD basics (0.2.4), bindr (0.1.1), bindrcpp (0.2.2), colorspace (1.3.2), compiler (3.5.1), crayon (1.3.4), datasets (3.5.1), dplyr (0.7.6), ggplot2 (3.0.0), glue (1.3.0), graphics (3.5.1), grDevices (3.5.1), grid (3.5.1), gtable (0.2.0), lattice (0.20.35), lazyeval (0.2.1), magrittr (1.5), methods (3.5.1), munsell (0.5.0), nlme (3.1.137), pillar (1.3.0), pkgconfig (2.0.2), plyr (1.8.4), purrr (0.2.5), R6 (2.2.2), Rcpp (0.12.18), reshape2 (1.4.3), rJava (0.9.10), rlang (0.2.2), scales (1.0.0), stats (3.5.1), stringi (1.1.7), stringr (1.3.1), tibble (1.4.2), tidyselect (0.2.4), tools (3.5.1), utils (3.5.1), withr (2.1.2), xlsx (0.6.1), xlsxjars (0.6.1), xtable (1.8.3).

The study will be conducted within the same environment or more recent versions.

5 Data

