6.2 Analysis Method

This section provides a detailed description of the statistical analysis that will be performed in this study.

Unless otherwise stated, all the statistical tests are two-sided at a significance level of 5%.

Summary statistics (number of observations, mean, 95% CI for mean, median, standard deviation and range) for all quantitative responses will be presented in tables. Frequency tables with number of observations, percentage of total will be created for all discrete responses.

Bar plots may be provided for some responses.

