8.2.5 Exploratory Objectives

Patient end needle breaking will be summarized as in Section [8.2.3](#).

Summary statistics for delivery time and total injection time will be presented as in Table [12](#). The average difference (BD PN - Terumo PN) in delivery time and total injection time will be evaluated as presented in Table [13](#).

Table 12: Summary Statistics for delivery time (Example only)

Pen Needle	N	SD	Mean	Median	Range
BD Nano	31	40.52	142.03	142.00	90,274
Terumo Nanopass	31	63.90	165.84	140.00	91,362

Table 13: Mean difference of Delivery time and Total injection time with confidence interval (reciprocal of number of seconds). The last column indicates whether superiority was met or not. (Example only)

	Mean difference	95% Lower bound	P value	Lower bound >0 (Superiority)
Delivery time	0.000739	-0.000180	0.113	Fail
Total injection time	0.000452	-0.000180	0.279	Fail

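### Score intervals for needle breaking and for per-needle percentages treat injections as independent, although each subject contributes six injections per needle in matched pairs

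*SAP*

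**What the plan says.** **Breaking, difference between needles.** SAP 6.2.4.2 summarizes the number and proportion of breaks per needle and adds that "a 95% confidence interval for difference in proportions will be calculated using the score method for independent proportions". It does not say which score interval is meant.

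**Per-needle percentages.** Protocol 13.3 plans frequency tables with "percentage of total and 95% confidence interval (score method) for the percentage (as applicable) will be created for discrete responses". SAP 6.2 is narrower: "Frequency tables with number of observations, percentage of total will be created for all discrete responses". However, the Table 9 layout in SAP 8.2.3 prints a 95% interval beside each needle's percentage. SAP 8.2.4 and 8.2.5 send binary leakage and breaking to the same layout ("Patient end needle breaking will be summarized as in Section" 8.2.3). Table 10 in that layout labels the difference as coming from a model, which does not agree with 6.2.4.2.

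**Design.** SAP 2.3 states: "Subjects are to perform 12 injections into the abdomen (6 pairs of injections"), and "each pair will contain one BD Nano™ PRO and one Terumo Nanopass® pen needle". SAP section 3 counts the yield: "50 Subjects will generate data for 600 pen needles: 300 pen needle pairs - 300 BD Nano™ PRO and 300 Terumo Nanopass".

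**Other comparisons.** Pain, force, bending, leakage and injection times are all analysed with a random subject effect (SAP 6.2.1 to 6.2.4.1).

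**The concern.** An interval for two independent proportions rests on two assumptions: the samples come from different units, and the injections within each sample are independent. The design breaks both, because the same subjects supply both needles and each supplies six injections per needle. Clustering is plausible. Subjects use their usual technique, and Protocol 6.2.1 allows angled insertion and skin pinch-up. Breaking is the only between-needle comparison of injection outcomes whose named method ignores the subject, and no reason is given.

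At stake is the honesty of the printed error limits. Protocol 9.2 makes a break that leaves cannula in the body an adverse event, so readers will look at this sponsor-versus-competitor comparison even though it is exploratory.

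**Working it through.** **1. The plan's own count.** 292 / 6 = 48.7, so 49 subjects, rounded to 50. Then 50 x 6 = 300 injections per needle, and 50 x 1.10 = 55 enrolled. These figures reproduce. The documents give no breaking rate, breaking interval or within-subject correlation (ICC), so the rates and ICCs below are assumptions. The 6.7% is the earlier Terumo leakage rate in SAP section 3, used only as an upper illustration.

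**2. Variance factors.** With six injections per needle per subject:
- One percentage: 1 + 5 x ICC. At ICC 0.1 this is 1.5, so the effective n is 300 / 1.5 = 200. At ICC 0.2 it is 2.0, so the effective n is 150. Standard errors rise by factors of 1.22 and 1.41.
- Difference at equal rates: 1 + 5 x ICC(within needle) - 6 x ICC(between needles). If the subject effect is specific to each needle, the last term is zero and the factor is 1 + 5 x ICC. If both needles share it fully, the factor is 1 - ICC. The independent interval is then too narrow in the first case and too wide in the second.

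**3. Coverage of nominal 95% intervals.** The simulation used 40,000 trials of 50 subjects x 6 pairs, with subject probabilities drawn from a beta distribution. The single-percentage interval is the Wilson score interval; the difference interval is Newcombe's, taken as the unspecified score method.

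| Interval | Rate | ICC 0 | ICC 0.1 | ICC 0.2 |
|---|---|---|---|---|
| One percentage | 0.3% | 93.9% | 90.3% | 88.4% |
| One percentage | 1% | 96.7% | 93.4% | 90.9% |
| One percentage | 6.7% | 95.0% | 89.3% | 84.0% |
| Difference, needle-specific clustering | 1% vs 1% | 97.0% | 93.2% | 89.0% |
| Difference, shared subject effect | 1% vs 1% | 97.1% | 98.0% | 98.7% |

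At equal rates of 0.3%, the difference interval covers 95.0% or more in every scenario tried, up to ICC 0.3.

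**4. What this does to printed limits.** For 3/300, the interval is 0.34% to 2.90% as planned and 0.27% to 3.57% with n = 200. For 0/300, the upper limit is 1.26% as planned and 1.88% with n = 200. For 0/300 against 5/300, the difference interval is -3.84% to -0.08% as planned. At ICC 0.1 it becomes -4.56% to +0.50% with needle-specific clustering and -3.69% to -0.20% with a shared effect.

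**5. Check of the repair.** Estimate the design effect from the subject counts as D = s² / (6 p (1 - p)), where s² is the variance of the counts across subjects and p is the pooled proportion. Set D to 1 if it is smaller, or if there are no events. Take five Terumo breaks, no BD breaks and 50 subjects, so p = 5/300:
- Five breaks in five subjects: s² = (5 - 0.5) / 49 = 0.0918, and D = 0.0918 / 0.0983 = 0.93, set to 1. The interval stays at -3.84% to -0.08%.
- Five breaks in one subject: s² = (25 - 0.5) / 49 = 0.50, and D = 0.50 / 0.0983 = 5.08. The effective n is 300 / 5.08 = 59. The Terumo limits become 0.29% to 8.95%, and the difference becomes -8.95% to +0.20%.

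In the same simulation, the adjusted per-needle interval covers about 94-96% at ICC 0.1-0.2. At equal 1% rates the adjusted difference interval covers 95.0% (ICC 0.1) and 93.3% (ICC 0.2) with needle-specific clustering. With a shared effect it covers 98.9% and 99.5%, so it remains conservative there.

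**The case against.** The strongest reply has four parts.

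- **Direction.** A reader might infer that the planned breaking interval overstates certainty. Poor technique, however, travels with the subject to both needles, and a shared effect makes the independent interval too wide. Too narrow an interval needs clustering that differs by needle, which nothing in the documents establishes. This stands.
- **Dramatic examples.** If one subject broke all six Terumo needles and no BD needle (0/330 against 6/330), the Newcombe interval would be -3.9% to -0.3%, while a subject-level t interval would run from -5.5% to +1.8%. That pattern is contrived, and general poor technique would not produce it. It illustrates the mechanism but does not measure the expected error.
- **Obvious remedies.** A subject-level t interval performs badly with few breaks. With true rates of 1% against 0% (55 subjects x 6), it covers 78% at ICC 0.1 and 72% at ICC 0.2. With 0.3% against 0%, it covers 55% and 48%. The unadjusted Newcombe interval covers 96-99% in the same cases. A percentile bootstrap cannot reach above 0 when no subject has a positive difference. This stands and shapes the fix.
- **Scope.** A reader might infer that the bending and leakage superiority tests share the fault. They do not: SAP 6.2.3 fits a random subject effect. Only their descriptive per-needle intervals are affected. Those rest on Protocol 13.3 (as applicable) and on Table 9, which is marked as an example and names no method. Breaking has no acceptance rule, and SAP section 7 plans no safety analysis.

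None of this makes an independent-samples method fit a paired, clustered design.

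**Conclusion.** The point holds as a minor one. The interval named in SAP 6.2.4.2 does not match the design. The score intervals of Protocol 13.3, if printed in the Table 9 layout, are too narrow under positive within-subject correlation. Their coverage is about 89-93% at ICC 0.1 and 84-91% at ICC 0.2, for rates of 1-6.7%. For the breaking difference no direction can be claimed. At equal 1% rates and ICC 0.1-0.2, coverage is about 89-93% with needle-specific clustering and about 98-99% with a shared subject effect. For very rare breaks (0.3%), the planned difference interval does not fall below 95%.

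All of these sizes depend on assumed rates and ICCs. No sample size, primary conclusion or secondary conclusion depends on the point.

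**What to change.** - **Per-needle percentages (Table 9 layout):** use the score interval with n divided by the design effect estimated from subject counts, floored at 1. State in SAP 6.2 that these intervals will be given, so that it agrees with Protocol 13.3.
- **Breaking difference (SAP 6.2.4.2):** replace the independent-samples method with a Newcombe interval built from these cluster-adjusted limits, and call it descriptive. Do not use a subject-level t interval or a percentile bootstrap.
- **Sparse events:** report the number of subjects with any break, per needle. If one needle has no breaks, state that its design effect is set to 1. If no needle breaks, give only counts and per-needle upper limits.
- **Consistency:** align SAP 6.2.4.2 with 8.2.5 and the model-based label in Table 10. Moving breaking to the logistic mixed model is not a safe way to do this. The SAP's own example output in 6.2.3 has a standard error of 2759378.

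The cost is a few lines of code and usually wider per-needle intervals. The adjusted difference interval does not exploit the pairing, so it stays too wide if the subject effect is shared by both needles. That is acceptable for a descriptive exploratory result.

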6.2.4.3 Non-Comparative Questionnaire

All the responses from Non-Comparative Questionnaire will be summarized with number and percentage of each option.

7 Safety Analysis

Data listings will be provided for any adverse events and serious adverse events in Appendix. The events will also be summarized descriptively per pen needle type. No safety analysis is planned.

8 Example Reports

This section provide examples of tables and graphical representations that will be provided in the study statistical report. These table examples were generated using the sample data available from the data base test framework which do not provide an exhaustive or representative example of the values and levels that will be obtained in the study. They are intended to provide illustrative examples of the tables and figures that will be included in the final statistical analysis report.

8.1 Study Execution

The number of subjects enrolled, randomized, withdrawn, who completed and who are excluded will be provided as in Table 1. More details on specific data may be provided in Summary Statistics and Appendix.

8.1.1 Analysis Population Set(s)

Table 1: (PP) Population Disposition (Example only)

Subject.Population	N	Comments
Subjects Enrolled	252	none
Subjects who did not meet I/E Criteria	6	none
Subjects Randomized	245	none
Subjects Withdrawn	5	none
Subjects who Completed the Study	240	none
Subjects Excluded from Analysis	1	Give Reasons

8.1.2 Data Exclusions

All exclusions will be listed with reason(s) for exclusion.

8.1.3 Executive Summary

A high level summary will be provided for each objective/endpoint (example below).

Primary Objective (examples only):

- *Injection Pain:* The lower bound of the CI for the average relative pain comparison between BD Nano™ PRO and Terumo Nanopass® met both non-inferiority and superiority criteria.

Secondary Objectives (examples only):

- *Injection force:* The lower bound of the CI for the average difference in rating of BD Nano™ PRO and Terumo Nanopass® injection force met the superiority criterion.
- *Needle Bending:* The upper bound of the CI for the average difference in percentage of needle bending occurrence with BD Nano™ PRO and Terumo Nanopass® met the superiority criterion.
- *Leakage:* The upper bound of the CI for the average difference in percentage of leakage occurrence with BD Nano™ PRO and Terumo Nanopass® met the superiority criterion.

In addition, a summary table for all primary and secondary objectives will be presented as in Table 2 (Example only). A blue check mark (✓) indicates that the acceptance criterion is met, while a red X mark (✗) indicates that the acceptance criterion is not met.

Table 2: Results Summary of primary and secondary objectives (Example only)

Objective	
Primary Objective	
Injection Pain (Non-inferiority)	✗
Injection Pain (Superiority)	✗
Secondary Objective	
Injection force	✓
Needle Bending	✓
Leakage	✓

8.2 Analysis and Results

8.2.1 Injection Pain

Summary statistics for the VAS scale will be presented as in Table 3.

The results for average relative VAS Score for BD Nano™ PRO vs Terumo Nanopass® will be evaluated as presented in Table 4.

Table 3: Summary Statistics for observed 150mm Relative VAS Scores (Example only)

	N	Mean	Std. Dev.	Mean 95% CI	Median	Median 95% CI	Range
Injection pain	13	12.12	44.00	(-74.13, 98.36)	15.00	(-71.25, 101.25)	-75, 67.5

Table 4: Fitted Average Relative VAS score for BD Nano vs Terumo Nanopass (Example only)

	Fitted Mean	CI	Non-Inferiority Conclusion (Lower bound CI > -10)	Superiority Conclusion (Lower bound CI > 0)
Injection pain	28.3	(17.1, 39.4)	TRUE	TRUE

[figure not shown]

Figure 2: Distribution of relative VAS scores with average and confidence interval per pen needle group and overall. Positive scores indicate that BD Next was preferred and negative scores indicate that the Current/Assigned PN was preferred. Note: This example graph comes from a study with different PN. Results for this study will reflect BD Nano performance.

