6.1 Derived Variables

6.1.1 Relative VAS Scale

After completion of each pair of injection, subjects will be asked to compare pain between the pen needles using a 150mm relative VAS Scale. Marks made on the 150mm relative VAS Scale are read using a 0 - 20 grid and the resulting discrete scores entered into the database. The results will be transformed to a [-75mm, 75mm] scale for analysis and reporting, where positive scores will reflect less pain for BD Nano Pro and negative scores will reflect less pain for Terumo.

Subjects will draw a vertical line on a relative VAS scale for each pair of injections, to indicate their relative pain perception for the pen needle used first or second in the pair. A vertical line drawn to the left of the center mark indicates that the 1st injection was less painful. A vertical line drawn to the right of the center mark indicates that the 2nd injection was less painful. A vertical line drawn at the center mark indicates no difference. Figure 1 shows an example of a 150mm (may not be to scale) relative VAS scale.

The scores are entered into the database on a discrete 0 – 20 scale. These scores will be transformed to a 150mm VAS on a [-75mm, 75mm] scale as follows:

Let $Y_{recorded}$ ($= 0, 1, \dots, 20$) be the recorded VAS score, the first transformation for the analysis of VAS score, $Y_{analysis}^*$ (mm), will be calculated as:

$$Y_{analysis}^* = \frac{150}{20} * Y_{recorded} - 75 \quad (1)$$

The sign of the VAS responses $Y_{analysis}^*$ will then be adjusted depending on which pen needle was used in the first and in the second injection, so that positive scores (+) will reflect less pain for BD Nano and negative scores (-) will reflect less pain for Terumo. Let $Y_{analysis}$ be the final relative VAS score used for the analysis. Then:

$$Y_{analysis} = \begin{cases} Y_{analysis}^*, & \text{if BD Nano is provided in the 2nd injection} \\ -Y_{analysis}^*, & \text{if BD Nano is provided in the 1st injection} \end{cases} \quad (2)$$

Which injection was less painful?

[figure not shown]

Figure 1: VAS Scale for Injection Pain

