6.2.1 Analysis of Injection pain

A two-sided 95% confidence intervals will be calculated for the average rating. A modeling approach will be used to adjust for the pair order effect, BD order effect within pair (due to the often-observed bias towards favoring the last pen needle used in a pair), abdomen site effect and random subject effect. Results will be tested for non-inferiority, followed by superiority:

- If the lower bound of the CI is $> -10\text{mm}$, we can conclude in non-inferiority.
- If the lower bound of the CI is $> 0\text{mm}$, we can conclude in superiority.

```

> #####
> ## Example R code to fit a linear model
> #####
> ##
> ## fitting the model
> library(lme4)
> model.fit=lmer(vas_analysis ~ BD_NANO_ORDER + PAIR_ORDER + ABDOMEN_SITE
+                  +(1|SUBJ_ID),
+                  data=dataset, na.action=na.omit)
>

```

```

> ## Example for estimated pen needle subgroup means
> ##      if the lower CL is > -10, non-inferiority is satisfied
> ##      if the lower CL is > 0, superiority is satisfied
> library(emmeans)
> emmeans(model.fit, ~1)

```

```

1          emmean      SE      df lower.CL upper.CL
overall  24.10616 3.666296 145.14 16.85993 31.35238

```

Degrees-of-freedom method: kenward-roger
 Confidence level used: 0.95

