8.3 Demographics and Diabetes History

Table 14: Subject Demographics (Example only)

Characteristic	Results
Gender	
Female	94 (50.8%)
Male	91 (49.2%)
Age	
Mean	55.8
95% Mean CI	53.9, 57.7
SD	13.0
Min, Max	20, 76
Observation Count	183
Missing Count	2
Total Count	185

Table 15: Distribution of Type of Diabetes (Example only)

Characteristic	Results
Diabetes Type	
Type II	152 (84.4%)
Type I	28 (15.6%)
Missing	2

Table 16: Diabetes History (Example only)

Characteristic	Results
Diagnosed year	
Mean	14.2
95% Mean CI	12.8, 15.6
SD	9.4
Min, Max	1, 54
Total Count	182
Injection Times per day	
once	74 (40.7%)
four	36 (19.8%)
twice	31 (17.0%)
five or more	19 (10.4%)
NA - injects non-insulin only	11 (6.0%)
three	11 (6.0%)
Pen needle used	
BD Nano 32Gx4mm	66 (36.5%)
NovoFine 32Gx6mm	33 (18.2%)
Other 32G	24 (13.3%)
Other 31Gx5mm	22 (12.2%)
NovoTwist 32Gx5mm	20 (11.0%)
NovoFine Plus 32Gx4mm	14 (7.7%)
Owen Mumford PenTips 32Gx4mm	2 (1.1%)
Missing	1
Injection site used	
Abdomen	158 (87.3%)
Thigh	14 (7.7%)
Arm	7 (3.9%)
Buttocks	1 (0.6%)
Other	1 (0.6%)
Missing	1

9 Appendix

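### Does the over-wide interval labelled as a 95% CI in SAP Table 3 call for a change to the plan?

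*SAP*

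**What the plan says.** SAP section 6.2 sets the rule for descriptive tables. They are to show "Summary statistics (number of observations, mean, 95% CI for mean, median, standard deviation and range) for all quantitative responses". A CI for the mean is listed; a CI for the median is not. Protocol section 13.3 lists no confidence interval at all among the descriptive statistics for quantitative responses.

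SAP section 8.2.1 then states: "Summary statistics for the VAS scale will be presented as in Table 3". The Table 3 row, marked as an example, gives N 13, mean 12.12, SD 44.00, mean CI (-74.13, 98.36), median 15.00, median CI (-71.25, 101.25) and range -75 to 67.5.

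SAP section 8 explains the status of all these tables: "These table examples were generated using the sample data available from the data base test framework". It adds that the sample data are not representative of what the study will yield, and then: "They are intended to provide illustrative examples of the tables and figures that will be included in the final statistical analysis report".

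The primary decision is defined elsewhere. SAP section 6.2.1 takes the lower limit of the interval from a mixed model with a random subject effect and compares it with -10 mm for non-inferiority and 0 mm for superiority. Table 4 is the reporting format for that result.

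**The concern.** Both upper limits in Table 3, 98.36 and 101.25 mm, lie beyond the +75 mm end of the scale and beyond the largest observed score of 67.5 mm. A CI for a median based on order statistics cannot exceed the observed maximum, and a mean of 12.12 with n = 13 and SD 44.00 cannot be that imprecise. The row looks as if the SD was used where the standard error belongs.

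This matters at first sight because the table summarises the primary endpoint and the SAP says the report will follow its format. If the same calculation were carried into the report, the error would grow with the square root of n. At the planned 300 pairs and the assumed SD of 50 mm, the half-width would be 1.96 × 50 = 98.0 mm instead of 98.0/√300 = 5.7 mm (ignoring correlation between pairs from one subject), a factor of √300 = 17.3. An observed interval reaching far below -10 mm would then stand beside a fitted interval that might pass, and readers could be confused about the main result.

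**Working it through.** **Inputs.** From SAP Table 3: n = 13, mean 12.12, SD 44.00, median 15.00 and the four printed limits. From SAP section 6.1.1, equation (1): scores are 7.5 mm × k, with k a whole number from -10 to 10.

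**1. Reproduce the printed limits.**
- Mean interval half-width: (98.36 + 74.13)/2 = 86.245.
- Median interval half-width: (101.25 + 71.25)/2 = 86.25.
- 1.96 × 44.00 = 86.24, so both half-widths are 1.96 × SD up to rounding.

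The grid allows a sharper check. The printed mean requires Σk = 21, because 7.5 × 21/13 = 12.1154. Given that, the printed SD requires Σk² = 447:

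7.5 × √[(447 − 21²/13)/12] = 7.5 × √34.423 = 44.0034.

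Then 1.96 × 44.0034 = 86.2467, and
- 12.1154 ∓ 86.2467 = -74.13 and 98.36;
- 15.00 ∓ 86.2467 = -71.25 and 101.25.

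All four limits match to two decimals. Other forms do not give 86.245: t × SD is 95.87, and a prediction interval has half-width 99.49 (t) or 89.49 (z).

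**2. What a CI for the mean would be.**

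| Form | Half-width | Interval (mm) | Printed ÷ correct |
|---|---|---|---|
| t, 12 df: 2.179 × 44.00/√13 | 26.59 | -14.47 to 38.71 | 3.24 |
| z: 1.96 × 44.00/√13 | 23.92 | -11.80 to 36.04 | 3.61 (= √13) |

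For the median, the 3rd to 11th ordered values of 13 give 97.8% coverage and the 4th to 10th give 90.8%. The raw scores are not printed, so the interval cannot be computed, but its upper limit could not exceed 67.5.

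**3. Does the same formula appear elsewhere in the SAP?**
- Table 14 (age): 1.96 × 13.0/√183 = 1.88, giving 53.9 to 57.7 as printed. The standard error is used.
- Table 16 (diagnosed year): 1.96 × 9.4/√182 = 1.37, giving 12.8 to 15.6 as printed. The standard error is used.
- Table 6 (injection force, same columns as Table 3): 1.4 ± 1.96 × 0.1 gives 1.204 to 1.596, but [-0.1, 2] is printed. It fits neither formula.
- Tables 5 and 8 hold placeholder figures: 132/330 is 40.0%, printed as 43.9%; 45.5 − 40.0 is 5.5, printed as 4.5.

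The SD-based interval can be identified in one row only.

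**4. Does it touch the decision interval?** The example output in SAP section 6.2.1 carries the note "Degrees-of-freedom method: kenward-roger" and prints estimate 24.10616, SE 3.666296 and 145.14 df. With t = 1.9764, 24.10616 ∓ 1.9764 × 3.666296 = 16.86 and 31.35, as printed. That output is a correct CI. Table 4 prints 28.3 (17.1, 39.4) without SE, df or N, so it cannot be checked in the same way.

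**The case for a change.** The best case for a change is that the example label excuses the data but not the arithmetic. The four-limit match shows that a calculation was run on real test scores rather than numbers typed in, so some code or spreadsheet contains the error. SAP section 8 says the examples illustrate the tables of the final report, and section 8.2.1 ties the VAS summary to Table 3. Correcting one calculation and one example table would cost almost nothing.

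Part of this stands. The row is wrong, it does not show what SAP section 6.2 asks for, and the disclaimer in section 8 concerns values and levels rather than formulas.

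The step from a wrong example to a wrong report does not stand. The SAP prints code for the models only, none for Table 3. Section 8 is assembled from several sources: Table 1 shows 252 enrolled and Table 14 shows 185 subjects against 55 planned, Figure 2 is said to come from a study of other needles, and Table 3 (mean 12.12) sits beside a Table 4 fitted mean of 28.3. Table 6, in the same format, does not share the pattern, and Tables 14 and 16 divide by √n. Reuse is possible but not shown, and the 17.3-fold figure depends on it entirely.

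Asking the descriptive row to allow for six pairs per subject, or to state t or z, is a preference. The decision model already has a random subject effect, and t and z hardly differ at about 300 pairs.

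**Conclusion.** The arithmetic point is correct: the two intervals in Table 3 are the estimate ± 1.96 × SD and are not confidence intervals. On the row's own figures the mean interval is 3.2 times (t) or 3.6 times (z) too wide. Those factors reflect 13 test records and do not measure any effect on this trial.

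No change to the plan follows. This is a clerical slip in an illustrative row. The governing instruction in SAP section 6.2 is already right, and an analyst who follows it will compute the mean interval from the standard error. The median interval is an extra column that neither SAP section 6.2 nor protocol section 13.3 calls for. Ordinary checking of table code before the report is issued should catch limits that run past the end of the scale. The non-inferiority and superiority conclusions come from the model-based interval, so sample size, error rate and decisions stay as they are.

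This conclusion assumes that the report follows the text of section 6.2 rather than the calculation behind the example. The documents do not settle that directly. If the assumption failed, the damage would be a misleading descriptive interval, with the primary result unchanged.
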